Study Design:	This project will be a multi-site retrospective cohort analysis of patients undergoing surgery for the indication of stress urinary incontinence for mid-term outcomes (1 year and greater) and long-term (2 years and greater) among both those with and without trans-vaginally placed synthetic mid-urethral slings (MUS).
Endpoints:	 This project seeks to provide a proof of concept for post-market medical device surveillance utilizing electronic health record data, in a use case of substantial public health safety interest to the FDA, patients, and health care providers: mid- and long-term adverse outcomes related to synthetic surgical mesh implantation for stress urinary incontinence. In pursuit of this goal, this proposal will: Assess data element availability among key covariates and exposures among patients undergoing surgery for stress urinary incontinence. If data are available, to assess rates of outcomes of re-operation for SUI, mesh erosion, re-operation for mesh revision or removal, chronic pain either as a new or worsening pain or requiring re-operation and voiding symptoms either as a new symptom or requiring re-operation, each with extended surveillance windows
	 after surgery. Provide a report of additional data elements important to conduct future device post-market surveillance in implantable devices for this indication, extrapolating to other device domains.

- 4) Lastly, if the data quality and volume are sufficient, we will develop a risk prediction model for the risk of the each of the outcomes stated above among patients receiving mesh for SUI.
- Statistical Methods: Each of the outcomes, exposures, and covariates will be summarized in aggregate for each site and a summarization and report will be provided to characterize the data at each site. Stratified reporting of those receiving surgery for SUI with synthetic mesh overall, SUI with synthetic mesh implantation by surgical approach, and SUI without mesh will be performed.

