However, by the mid-2000's, a growing number of adverse event reports had been submitted to the MAUDE FDA database related to trans-vaginal synthetic mesh products used for these indications. During 2005-2010, MAUDE received 1371 reports of injury, death, and malfunction of mesh for SUI treatment, related to mesh erosion, pain, infection, recurrence of urinary symptoms, and organ perforation, along with a 5-fold increase in MAUDE reporting rates in 2008-2010 compared to 2005-2007. While these numbers increased scrutiny surrounding these devices, a lack of denominator data and a reliance on voluntary reporting that is sensitive to FDA and press scrutiny limit the interpretability of these findings.

Risk assessments around synthetic surgical mesh for SUI remains uncertain for some outcomes extending beyond one year²⁵. [name] and colleagues evaluated a New York State prospective registry (SPARC) that included all surgeries and evaluated 41,604 women undergoing mesh implantation for pelvic organ prolapse or stress urinary incontinence. Among the 22,252 women undergoing surgery for SUI, 1.6% of them had mesh erosions that required intervention²². In one UK study, overall re-operation rates were only 3.2% among mid-urethral sling procedures for SUI after a median 2.8 years of follow-up²⁶. In a private US claims database, the cumulative re-operation rate was 14.5% after a median 9 years of follow-up²⁷, with sling revision/removal at 3.7%²⁸. Other small studies in non-US populations have shown low rates of long-term complications (1-3%)²⁹. A recent UK study among 95,057 women and a median follow-up time of 5.5 years found that risk of re-operation was 2.6% at 1 year, 5.5% at 5 years, and 6.9% at 9 years³⁰. More specifically, mesh removal rates were 3.3% at 9 years in this population. Another UK study among 92,246 patients with first time mesh implantations for SUI found a 5-year complication rate of 9.8%³¹. A Canadian study of 59,887 women found ~3.5% may require mesh removal or revision within 10 years of initial surgery³².

There have also been some systematic reviews and meta-analyses done attempting to further understand the complications in this population. In 2015, a systematic review of studies with a follow-up of 36 months for TOMUS and 60 months for RPMUS were searched and studies comparing the two were

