3. STUDY OBJECTIVES

There remains uncertainty with regards to longer term outcomes among women receiving mesh slings for stress urinary incontinence, and this project seeks to address knowledge gaps for long term outcomes among mesh implantations by leveraging electronic health record data across 5 participating health systems.

Specific Aims: This project seeks to provide a proof of concept for post-market medical device surveillance by assessing the capacity of routinely collected electronic health record data to evaluate the long-term adverse outcomes related to synthetic surgical mesh implantation for stress urinary incontinence.

In pursuit of this goal, this project will:

- 1) Assess data element availability among key covariates and exposures among patients undergoing surgery for stress urinary incontinence,
- 2) If data are available, to assess rates of outcomes of mesh erosion, re-operation for SUI, reoperation for mesh revision or removal, chronic pain either as a new or worsening pain or requiring re-operation and voiding symptoms either as a new symptom or requiring reoperation, each with extended surveillance windows after surgery.
- 3) Specifically, this project will evaluate mid-term (>1 year) and long-term (>2 years) adverse events following synthetic surgical mesh implantation (mid-urethral slings) for female SUI.
- 4) Lastly, if the data quality and volume are sufficient, we will develop a risk prediction model for the risk of the each of the outcomes stated above among patients receiving mesh for SUI.

In summary, this project seeks to better understand the safety of mesh used for stress urinary incontinence by leveraging electronic health record data. The FDA intends on incorporating these data into its growing portfolio of evidence in order to help support regulatory decision making on level of risk

for these procedures and recommendations around use of mesh for this indication. This study has the potential to increase medical knowledge regarding these devices.

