7. STUDY OUTCOMES

The primary outcomes of interest are:

- Re-operation (revision, incision, excision, removal) or mesh removal
- Chronic pain, defined as pain persisting at least three months after surgery⁴⁹
- Voiding symptoms, defined as recurrence of incontinence or new retention.

All outcomes are determined in the surveillance period after surgery. Re-operation or mesh removal is defined as a surgery for any kind of mid-urethral sling, urethral bulking agent, bladder neck pubovaginal sling (autologous or allograft), or revision for mesh exposure. Resumption of voiding symptoms was defined as subsequent urinary retention, urinary incontinence, and sling revision for urinary retention. Chronic pain is defined as a new post-operative pain score >3 of 10 on vital sign data occurring over at least 3 months or greater of duration, or diagnosis codes related to abdominal and pelvic pain.

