		 Mesh exposure and erosion (ICD9/10 629.31, 629.32/T83.711, T83.721) Urinary Retention (CPT Code 53500, ICD 9/10 788.20, 788.21/R33.0, R33.8-R33.9) Urgency of urination (ICD9/10 788.63/R39.15) Urge incontinence (ICD9/10 788.31/N39.41) Bowel injury (ICD9/10 569.83/S36) Bladder/urethral injury (ICD9/10 596.6,867.0/S37) Infection (ICD9/10 686.9,998.5,999.3,998.51,998.59/T81) Retropubic hematoma (ICD 9/10 568.81,,568.81,459.0/K66.1) Retopubic hematoma (ICD 9/10 568.81,,568.81,459.0/K66.1) Retopubic hematoma (ICD 9/10 568.81,568.81,459.0/K66.1) Bulking Injection CPT 51715, ICD 9/10 59.72/ PCS 3E0K3GC Laparoscopic Retropubic Urethropexy CPT 51990, 51992, 51999 Abdominal Retropubic Urethropexy CPT 51840,51841 Needle Bladder Neck Suspension CPT 51845 Kelly plication CPT 57220 Cystourethroplasty CPT 51800 Subtypes: Stress incontinence, female/mixed incontinence (ICD9/10 625.6,788.33/N39.46) Stress incontinence (female) (male)(ICD10 CM N39.3) 		
Outcome	Mesh Removal	 General, CPT 57287-Removal or revision of sling for stress incontinence (fascia or synthetic) ***some erosions managed surgically may have been coded by a different CPT (i.e. 57295 revise vaginal graft via vaginal approach) and not CPT 57287, which indicates a sling revision/removal. 	Yes	Possible Options: (a surgery for any kind of mid-urethral sling, urethral bulking agent, black neck pubovaginal sling (autologous or allograft), or revision for mesh exposure). Represented as a Date, allows time-to-event analysis.
Outcome	Post-Procedural Pain	?, mix of vital sign (pain score >3 of 10 on vital sign data) and likely free text. Also, diagnosis codes related to abd/pelvic pain (if prior pain free).	Some portion	Would have to exclude prior chronic pain or detect specific mention of new pain (free text). Could analyze group with no pre-surgical pain,

Protocol 1				[15 July 2020]
				otherwise probably beyond scope. Date/Time of first post- op occurrence.

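### The Section 7 primary outcome pools repeat incontinence surgery with revision for mesh exposure only, so as written it is not the mesh revision/removal rate that Aim 2 asks for

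*Protocol*

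**What the plan says.** The protocol describes this outcome in four places.

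- **Section 7, bullet.** One primary outcome: "Re-operation (revision, incision, excision, removal) or mesh removal". No reason for the revision or removal is required.
- **Section 7, defining sentence.** "Re-operation or mesh removal is defined as a surgery for any kind of mid-urethral sling, urethral bulking agent, bladder neck pubovaginal sling", continuing "autologous or allograft), or revision for mesh exposure". The next sentence deals with a different primary outcome: "Resumption of voiding symptoms was defined as subsequent urinary retention, urinary incontinence, and sling revision for urinary retention".
- **Aim 2 (Section 3) and synopsis.** Aim 2 will "assess rates of outcomes of mesh erosion, re-operation for SUI, reoperation for mesh revision or removal". The synopsis makes the same separation: "assess rates of outcomes of re-operation for SUI, mesh erosion, re-operation for mesh revision or removal". Aim 4 then promises a risk model for each outcome on that list.
- **Appendix (Section 13).** The Re-Operation row has its own block for mesh revision/removal (CPT 57287, 10120 and ICD-10-PCS codes). Its subtypes by reason include bleeding, nerve injury, pain, exposure/erosion, retention and infection. Incontinence procedures are listed separately in the same row. A further row, Mesh Removal, is defined by CPT 57287 and captured as a date. Its Notes cell, however, repeats the pooled Section 7 wording under the label Possible Options. Its definition cell warns that "some erosions managed surgically may have been coded by a different CPT (i.e. 57295 revise vaginal graft via vaginal approach") without saying whether that code counts.

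Sections 4 and 6 both state that the primary outcomes are those defined in Section 7.

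**The concern.** A second incontinence procedure mainly records that the first did not hold. Revision or removal of the sling records a problem with the device. The protocol's purpose is device safety, and Sections 3 and 11 say that the FDA may use the results in regulatory decisions. If analysts follow Section 7 literally, the headline safety outcome counts second slings and bulking injections, and leaves out a sling removed for pain or infection. The resulting rate could not be set beside the removal rates in Section 1.1, such as "mesh removal rates were 3.3% at 9 years in this population". Each site processes its own data, and the Cox models in Section 9.1 are fitted to each of the outcomes, so an unsettled definition carries through to the site-level data and the models.

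**Working it through.** The protocol states no event count, power or expected rate for this outcome, so there is no planned figure to reproduce. The check compares definitions, with a short calculation for scale.

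**Step 1: what each text counts.**

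| Event | Section 7 bullet | Section 7 defining sentence | Aim 2 / synopsis | Appendix |
|---|---|---|---|---|
| New sling or bulking agent | re-operation, pooled | yes, pooled | SUI re-operation | bulking among the incontinence procedures |
| Revision for mesh exposure | yes, pooled | yes, pooled | mesh revision/removal | revision/removal block, subtype |
| Revision or removal for pain or infection | yes, pooled | not named | mesh revision/removal | revision/removal block, subtype |
| Revision for retention | yes, pooled | not named here; listed under voiding symptoms | mesh revision/removal | revision/removal block, subtype |

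Three conflicts follow. The defining sentence is narrower than the bullet it explains. Both pool what Aim 2 and the synopsis keep apart. The appendix separates the two and accepts many reasons for revision, but its Mesh Removal Notes bring the pooled wording back, so a second sling could be counted as a mesh removal.

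The defining sentence also does not name the urethropexy, needle suspension and Kelly plication procedures that the appendix lists for incontinence, so the SUI side does not match its code list either.

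**Step 2: scale, for illustration.** Inputs from Section 1.1: UK cohort at 9 years, re-operation 6.9% and mesh removal 3.3%; US claims, re-operation 14.5% (median 9 years) and sling revision/removal 3.7%. The protocol does not say whether removals are included in the re-operation rates, so both readings are shown.

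If removals are a subset of re-operations, share = removal / re-operation:
- UK: 3.3 / 6.9 = 47.8%; pooled rate is 6.9 / 3.3 = 2.1 times the removal rate.
- US: 3.7 / 14.5 = 25.5%; 14.5 / 3.7 = 3.9 times.

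If the two are disjoint, share = removal / (re-operation + removal):
- UK: 3.3 / (6.9 + 3.3) = 3.3 / 10.2 = 32.4%; 10.2 / 3.3 = 3.1 times.
- US: 3.7 / (14.5 + 3.7) = 3.7 / 18.2 = 20.3%; 18.2 / 3.7 = 4.9 times.

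Removals would therefore be about 20% to 48% of pooled events, and the pooled rate about 2 to 5 times the removal rate. This places every removal in the pool. The literal Section 7 sentence would admit only those for exposure, so the share under that reading would be lower; the protocol gives no figure from which to say by how much.

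**The case against.** The strongest reply is that the appendix already does the work. It has a revision/removal block that is not limited by reason, reason subtypes, separate incontinence procedure codes and dates for time-to-event analysis. Aim 4 promises a model for each outcome on the list that separates the two. The Section 7 bullet puts no limit on the reason. The pooled text in the Mesh Removal row is only a working note.

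Much of this stands, and it rules out several stronger readings.

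- A reader might infer that the study cannot deliver the removal rate. It can: the appendix codes would yield it.
- A reader might infer that revision for retention has been taken out of re-operation. Section 7 places it under voiding symptoms but does not say that it counts only there, and the appendix lists it as a revision subtype.
- A reader might infer that 57295 is excluded, or should simply be added. The first is unresolved rather than decided. As to the second, the appendix's procedure list describes 57295 as revision of a prosthetic vaginal graft, and Section 4 includes patients with concomitant surgery, so unqualified use could pick up revisions of prolapse mesh.
- A reader might argue that the two event types have opposing predictors. Nothing in the protocol documents that, and the point does not need it.

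The reply fails on which text governs. Sections 4 and 6 name Section 7, not the appendix. Section 7 contradicts the appendix and the aims, and the appendix row for Mesh Removal points both ways.

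**Conclusion.** The point holds as an error in the definition of a primary outcome. Section 7 as written does not define either of the two outcomes in Aim 2 on its own, and its defining sentence gives something other than the mesh revision/removal rate. It does not show that the planned data are inadequate, since the rate is recoverable from the appendix codes.

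The size (removals about 20% to 48% of pooled events) is illustrative only. It assumes that the re-operation and removal rates within each source refer to comparable populations and follow-up. The two US rates carry separate citations, and no separate time horizon is given for the 3.7%. The conclusion rests on the conflicting texts and does not depend on these figures.

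**What to change.** In Section 7, replace the pooled outcome by two primary outcomes, each tied to its full appendix code block:

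- (a) sling or mesh revision or removal for any reason (57287, 10120 and the listed ICD-10-PCS codes), with the reasons reported as subtypes;
- (b) re-operation for SUI: every incontinence procedure code that the appendix Re-Operation row lists (51715, 51990, 51992, 51999, 51840, 51841, 51845, 57220, 51800), plus new sling procedures.

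Then:

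- Fit and report (a) and (b) separately; any composite is additional.
- State whether revision for retention counts in (a), in voiding symptoms or in both.
- Count 57295 only with a qualifier that ties it to the sling, for example in a sensitivity analysis.
- Delete the pooled Possible Options text from the Mesh Removal row.

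The change is to wording and code lists, nearly all of which the appendix already contains. The real cost is fewer events per model, which matters most for the LASSO Cox fits at the smaller sites.

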4. STUDY DESIGN

This project will be a multi-site retrospective cohort analysis of trans-vaginally placed synthetic midurethral slings (MUS) implanted in patients for the indication of stress urinary incontinence for mid- and long-term outcomes (1 year and greater). We will identify all patients at each of the sites that have received a MUS through administrative and device implantation data. The key exposures will be MUS devices identified by administrative codes. Because ascertainment of the surgical approach is critical to the evaluation of post-operative complications, and has differing rates depending on the approach, we will determine which approach was used: Retropubic MUS (RPMUS), Transobturator MUS (TOMUS), Single-Incision Sling (SIMUS), or Adjustable Sling (AMUS). In prior work at Mayo, determination of the surgical approach was present in 100% of cases in the operative notes. We will also identify all patients that received a surgery for SUI without mesh (autologous or cadaveric fascial sling or burch colposuspension or bulking agents) and evaluate the same outcomes of interest in that population separately to provide an indirect comparison group. No direct comparison of mesh and non-mesh groups will be conducted. Patients with concomitant surgeries at the time of trans-vaginal mesh implantation for SUI will be included. The primary outcomes of interest are long-term safety outcomes relevant to these devices and defined in Section 7. In addition, using the Mayo Clinic data, we will be able to validate the electronic data with the manually curated data from 2010-2012². We will leverage this data to better understand how much of the data can be electronically generated and where additional information would need to be collected in an electronic environment.

Beyond the variables collected for exposures, outcomes, and cohort inclusion/exclusion, important covariates relevant to the device exposures and outcomes, and present prior to the surgery, will also be collected.

These include:

- Patient demographics
- Chronic pain
- Prior abdominal surgery
- Receipt of urodynamic testing (structured data will not have the results)
- BMI
- Insurance payer

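### The protocol gives conflicting definitions of the primary chronic-pain outcome and fixes no matching at-risk population, so the pain rate and the baseline-pain coefficient can be biased in either direction

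*Protocol*

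**What the plan says.** The protocol describes the pain outcome in four places, and they differ.

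- **Synopsis and Section 3, Aim 2:** "chronic pain either as a new or worsening pain or requiring re-operation".
- **Section 7, list of primary outcomes:** "Chronic pain, defined as pain persisting at least three months after surgery". There is no newness condition.
- **Section 7, operational paragraph:** "Chronic pain is defined as a new post-operative pain score >3 of 10 on vital sign data occurring over at least 3 months", followed by an alternative route, "or diagnosis codes related to abdominal and pelvic pain". Newness is attached to the score arm only, and there is no rule for worsening.
- **Appendix, Post-Procedural Pain row:** the code route is "diagnosis codes related to abd/pelvic pain (if prior pain free"). The notes column adds "Would have to exclude prior chronic pain or detect specific mention of new pain (free text") and "Could analyze group with no pre-surgical pain", and treats anything else as probably out of scope.

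On who is at risk, Section 4 lists chronic pain among the "important covariates relevant to the device exposures and outcomes, and present prior to the surgery", so women with prior pain are expected in the cohort. None of the four exclusions in Section 5 concerns pain. Section 9.1 runs a Cox model for each outcome from the date of surgery and states no risk set specific to pain.

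**The concern.** A new-onset outcome needs a population that can have a new onset, and the same newness test has to apply to every route by which an event is counted. Here the test differs between the aims, the two arms of Section 7 and the appendix, and the population is left open. Two programmers working from this protocol could legitimately produce different event counts. A woman whose score goes from 4 to 8 for three months is an event under Aim 2. She is not one under the Section 7 score arm, because a score above 3 is not new for her. She is one under the Section 7 code arm if a pelvic pain code is entered after surgery. She is not one under the appendix's version of the code arm.

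Chronic pain is one of the primary safety outcomes. The FDA intends to use the data in regulatory decisions (Section 3), and the final prediction models are to be shared (Section 11). Both the reported rate and the baseline-pain coefficient depend on how this is resolved.

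**Working it through.** The protocol states no pain rate, event count or sample size for this outcome, so there is no figure of its own to reproduce. The check is simple algebra on assumed inputs.

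**Inputs (none given in the documents)**
- f = share of women with baseline pain: 10–30%.
- r = risk of new chronic pain in women without baseline pain: 3–10%.
- q = probability that a woman with baseline pain is counted as an event: 0, or 3–50%.

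**Formulas**
- Reported risk = (1 − f)·r + f·q. The target, new pain among women who can have it, is r.
- Approximate hazard ratio for baseline pain = ln(1 − q) / ln(1 − r).

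**Reading A.** Newness governs both arms, as the appendix has it for codes, and women with baseline pain stay in the denominator, since Section 5 does not remove them. At the limit q = 0, the reported risk is (1 − f)·r, a relative dilution equal to f. With f = 20% and r = 5%: 0.80 × 5% = 4.0%. The hazard ratio tends to 0.

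**Reading B.** Section 7 is applied literally, so a carried-over pain code after surgery counts. With f = 20% and r = 5%:
- q = 3%: 4.0% + 0.6% = 4.6%; hazard ratio ln(0.97)/ln(0.95) ≈ 0.59.
- q = 20%: 4.0% + 4.0% = 8.0%; hazard ratio ln(0.80)/ln(0.95) ≈ 4.35.
- q = 50%: 4.0% + 10.0% = 14.0%; hazard ratio ln(0.50)/ln(0.95) ≈ 13.5.

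Reported risk across the assumed range:

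| f | r | A (q = 0) | B, q = 3% | B, q = 20% | B, q = 50% |
|---|---|---|---|---|---|
| 10% | 5% | 4.5% | 4.8% | 6.5% | 9.5% |
| 20% | 5% | 4.0% | 4.6% | 8.0% | 14.0% |
| 30% | 5% | 3.5% | 4.4% | 9.5% | 18.5% |
| 20% | 3% | 2.4% | 3.0% | 6.4% | 12.4% |
| 20% | 10% | 8.0% | 8.6% | 12.0% | 18.0% |

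The break-even is q = r. Below it the rate is diluted and baseline pain looks protective. Above it, when women with prior pain are re-coded more often than pain-free women are newly coded, the rate is inflated and baseline pain looks harmful. The baseline covariate and the outcome's code arm both cover pelvic pain, so carry-over is plausible, but its frequency is unknown.

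**Reading C.** The appendix note is followed in full and women with prior chronic pain are removed. The reported risk is then r. Worsening pain is still not measured, and baseline pain cannot serve as a predictor for this outcome.

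**Can free text settle it?** The appendix's alternative is to find mentions of new pain in notes. Section 8.1 extracts documents within 2 days either side of the procedure code and keeps the pre-operative planning note and the operative note. Those cannot show pain that begins or persists months later. Chart review of 50 to 100 cases per site (Section 6) is for validation only.

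**The case against.** A reader might infer something stronger: that Section 7 counts only new pain, that women with prior pain therefore cannot have the event, and that the rate is necessarily understated and baseline pain protective by construction. The documents do not support this, for three reasons.

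- The sentence that requires a new score goes on to admit diagnosis codes with no such condition, and the headline bullet has none either.
- Even on the score arm, zero events does not follow. The appendix defines baseline chronic pain by diagnosis codes and possibly pain medication, while the score arm uses vital-sign scores. A woman with a prior dyspareunia or leg-pain code but low recorded scores can still have a new score above 3. Aim 2 also admits pain that requires re-operation.
- Reaching that conclusion means taking the numerator restriction from the appendix while setting aside the note in the same row about excluding these women. No passage states that combination.

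These points stand. They remove any claim to a known direction, but they do not remove the conflict.

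It can also be said that a risk set may be left to an SAP, that modelling depends on data sufficiency, and that LASSO may not keep baseline pain. The first has some force for the risk set alone, but not for a primary outcome that one protocol defines in incompatible ways. The other two concern only the model, and the Aim 2 rates are affected without it. The magnitudes above do rest entirely on assumed inputs. A worsening rule would also need serial scores, which may not be available: one site's comment in the appendix expects the post-operative pain variable to need free text.

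**Conclusion.** The point holds as an unresolved conflict with bias of unknown sign. Aim 2 and the synopsis, the Section 7 headline, the two arms of the Section 7 rule and the appendix do not describe the same outcome, and no at-risk population is fixed to go with any of them.

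At an assumed 5% new-pain risk and 20% baseline pain, the reported rate is 4.0% if newness governs both arms and women with baseline pain are kept. It is 8.0–14.0% if codes are taken literally and 20–50% of those women are re-coded. The baseline-pain hazard ratio moves from near 0 to about 4.35–13.5. In the first case the relative dilution is at most the baseline-pain share, 10–30% on the assumed range. Only restriction to women without baseline pain, which the appendix raises tentatively, recovers the 5%. The shares and risks are assumptions. That different passages give different event counts is not.

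**What to change.** - **One newness rule.** In Section 7 and the appendix, apply the newness condition to both scores and codes, with a stated pre-operative look-back. The documents fix no length for it; the sponsor should choose one and say why.
- **One population for new pain.** Analyse new chronic pain only in women with no baseline pain code and no pre-operative score above 3 in that look-back. Use those women as the denominator and the Cox risk set, and leave baseline pain out as a predictor for this outcome.
- **A separate stratum.** Report women with baseline pain on their own. Add a worsening rule, stated in advance, only if serial pre- and post-operative scores are available. Otherwise delete worsening from the synopsis and Aim 2 and label the result as new pain in women without baseline pain.
- **Consistency.** Bring the Section 7 headline bullet into line with the operational rule.

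The cost is wording in the synopsis, Aim 2, Section 7 and the appendix, plus one stratified report using codes and scores already planned for collection. The new-pain analysis will have fewer women, and those without a pre-operative score will be classified by codes only. The worsening rule is the one element that could need data the sites may not hold, which is why it is conditional.
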